**1) Protocol Title**

High stimulation rate ABR in ASD and non-ASD children

**2) Objectives\***

The purpose of this proposal is to develop and assess the feasibility of an automated auditory brainstem response (ABR) based neurological screening device and software module that will provide early detection of increased risk for autism spectrum disorder (ASD) and other neurological conditions (e.g., speech impairment or sudden infant death syndrome (SIDS)). Recordings will be obtained at a range of stimulation rates from 19 to 250/second to determine the optimal rate to be used for newborn screening.

**3) Background\***

ASD is characterized by persistent deficits in communication and social interaction across multiple contexts and restricted, repetitive patterns of behavior, interests, or activities. Symptoms cause clinically significant impairments in social, occupational, or other important areas of current functioning. The term “spectrum” refers to the wide range of symptoms, skills, and levels of impairment or disability that children with ASD can have. Some children are mildly impaired by their symptoms, while others are severely disabled.

The incidence rate of ASD is 1:59. Based on 3.94 million births in the United States in 2016, 66,780 new cases of ASD will be diagnosed from that birth cohort alone. Although the incidence rate of hearing loss is 3:1000, over 5 times smaller than ASD, universal hearing screening has been instituted in most states for more than 20 years. Approximately 2 million babies per year are currently screened with ABR technology, one million with Intelligent Hearing Systems (IHS) equipment alone. Current screening protocols use moderate auditory stimulation levels, 35 dB nHL, to focus on hearing sensitivity. The typical testing time is approximately 7 minutes plus electrode and insert earphone placement time. The new system tested in this study will add a supra-threshold testing level required for neurological evaluation, and will introduce only an additional minute to the screening process. These additions will capitalize on the initial prep-time and cost of disposables used for hearing screening, while providing important information on the newborn’s neurological status at almost no additional cost. Not screening for neurological conditions at this stage represents an enormous loss of opportunity to provide early diagnosis and intervention to these infants. Substantially improved outcomes can be achieved through early diagnosis and intervention.

The practice of early screening and identification of ASD is encouraged by the nation’s Healthy People 2020 objectives and the American Academy of Pediatrics. Although ASD symptoms are present in the early developmental period and can be recognized in the first two years of life, the median age of ASD diagnosis still remains older than 4 years and has not decreased in recent years

(Brett et al., 2016). Recommendations from the Autism and Developmental Disabilities Monitoring Network (ADDM) include enhancing strategies to address the need for decreasing the age when children receive their first evaluation for and a diagnosis of ASD and are enrolled in community-based support systems (Baio, 2014). Given that about 46% of children with ASD have average to above average intellectual ability (Baio, 2014), early intervention provides a significant opportunity to improve the outcomes of these individuals in particular, as well as those with more severe intellectual disabilities.

The system developed will serve to provide an objective measure of neurological function that can be used for screening purposes at any age to determine the transmission rate and synchrony of neurological pathways. Of particular interest is the reported link between ABR peak latency delays and ASD (Dabbous, 2012; Fujikawa-Brooks et al., 2010; Kwon et al., 2007; Maziade et al., 2000; Miron et al., 2015; Rosenhall et al., 2003; Roth et al., 2012; Russo et al., 2010; Tas et al., 2007; Thivierge et al., 1990; Wong et al., 1991). Although evoked potentials can be acquired using visual and somatosensory stimulation; auditory stimulation provides an ideal method as it requires no patient participation and is painless. Tests using ABR can be conducted in a minimally invasive procedure by only applying three surface scalp electrodes and sound stimulation while an infant is in natural sleep. Newborn hearing screening is currently routinely conducted universally across the United States and in many developed countries around the world using the same ABR technology. Expanding hearing screening to neurological screening could be accomplished with minimal cost and test time using the proposed techniques.

Significant latency differences in the peak components of ABRs have been identified in children with ASD compared to aged matched normal children (Dabbous, 2012; Fujikawa-Brooks et al., 2010; Kwon et al., 2007; Maziade et al., 2000; Rosenhall et al., 2003; Roth et al., 2012; Russo et al., 2010; Tas et al., 2007; Thivierge et al., 1990; Wong et al., 1991). Studies have also shown that prolonged ABRs occurred in infants who later had social engagement problems (Geva et al., 2011) and repetitive behaviors (Cohen et al., 2013). More recently, Miron et al. (2015) showed that prolonged ABR occurred in young infants later diagnosed with ASD and that this prolongation, especially in wave V, was capable of accurately classifying ASD. Although the sensitivity (84% & 80%) and specificity (56% & 70%) measures for Cohen et al. (2013) and Miron et al. (2015), respectively, are encouraging, the resulting high false positive rate would be of concern for any screening tool. It is important to point out that these values were derived primarily from testing at-risk infants and that a broader study including a large number of well-babies is required to fully develop latency norms and new specificity and sensitivity measures.

There are several options to improve test sensitivity and specificity. Choosing the proper cut-off value for absolute and interpeak latency difference between normal and ASD infants are critical for optimizing any

screening tool. In addition to abnormalities in ABR latencies, studies have shown that ABR amplitudes are also abnormal in some children with ASD (Coutinho et al., 2002; N. Russo et al., 2009). Miron et al. (2015), hypothesize that predicting ASD based on both ABR amplitude and latency may be even more accurate than predicting based solely on ABR latency. Furthermore, the use of higher stimulation rates may provide an additional way to differentiate normal versus ASD infants.

#### **4) Inclusion and Exclusion Criteria\***

Subjects will be children between the ages of 1.5 and 5.5 years. Our target age group is 3.5 to 4.5 years of age but younger or older children may be included as well. Parents must be able to communicate effectively in English to participate in the study.

A formal ASD diagnosis (i.e., community diagnosis or educational eligibility diagnosis) is required for children to be part of the ASD group. Children in the control group will not have a diagnosis of ASD or any other developmental disability. Control children will be age and gender matched with the ASD subjects. All children will be screened to insure that they do not have hearing problems, a history of middle ear infections, or a current ear infection. All children will be given an Otoacoustic Emissions (OAE) hearing screening test prior to ABR testing to confirm that their peripheral auditory system is normal.

Exclusion criteria for all subjects include: hearing problems, history of middle ear infections or current ear infection, and other abnormalities or impairments that could impact neurological functioning such as seizures, comorbid syndromes or diseases, sensory disorders, craniofacial abnormalities, other developmental or physical disabilities, or having a sibling with ASD or another developmental disability.

#### **5) Procedures Involved\***

Data collection is anticipated to occur from September 2019 through May 2021.

##### Phone Screen:

Parents/guardians who call to inquire about the study will be screened over the phone to determine if they meet the inclusion criteria. Subjects who meet inclusion criteria will be invited to come to the lab. The Phone Intake Form is attached.

##### Lab Session:

All assessments will be completed during one lab visit. A second visit may be needed if testing cannot be completed during the initial visit. The lab session will include some or all of the following assessments:

*Informed Consent:*

The study will be described to the parent/guardian and informed consent will be obtained. The Informed Consent document is attached.

*Head Circumference:*

The circumference of the child's head will be measured using a measuring tape.

*OAE:*

In order to make sure that the subject has normal hearing, an Otoacoustic Emissions (OAE) measurement will be conducted. OAEs are a routine audiometric test conducted to measure cochlear function. OAEs will be recorded using the SmartDPOAE system on the Duet Platform (Intelligent Hearing Systems Corp). The OAE procedure involves placing a small probe in the ear, similar to an insert earphone, presenting soft sounds to the ear at 65 and 55 dB SPL and measuring the acoustical output from the ear. The OAE system provides a pass or refer output based on the measurements. Children with passing OAE results will be retained for the ABR portion of the study.

*ABR:*

Neurological function will be assessed using ABR. ABRs will be recorded using the SmartEP system on the Duet Platform (Intelligent Hearing Systems Corp). Various stimulation rates (19-250/sec) using a 75 dB nHL100  $\mu$ sec click will be used to compare ABR peak latency and amplitude differences between children with ASD and control children. The ABR procedure involves placing 4 small electrodes (Ambu Neuroline 720) on the subject's head (right and left mastoids, high and low forehead) and inserting earphones in both ears. Prior to placing the electrodes, a disposable electrode prep pad (70% isopropyl alcohol, purified water, and pumice) will be used to gently clean the skin at the electrode site. Click sound stimuli of a moderate level (75 dB nHL) are presented at various stimulation rates. This intensity level is routinely used for hearing assessment and is considered safe for short duration stimuli. ABR data will be recorded and peaks identified and measured. A flyer describing the SmartDPOAE and SmartEP systems is attached.

*ASRS*

All children, including controls, will be evaluated using the Autism Spectrum Rating Scale (ASRS) questionnaire to verify ASD symptomology in the ASD children and lack of symptomology in the control children. The ASRS will be completed by the child's parent or guardian. A sample of the ASRS questionnaire is attached.

*ASQ-3:*

The Ages and Stages Questionnaire, Third Edition (ASQ-3) will be used to evaluate the child's development in the areas of communication, gross motor, fine motor, problem solving, and personal-social. The ASQ-3 will be completed by the child's parent or guardian. A sample of the ASQ questionnaire is attached.

*Family Information Form:*

The Family Information Form contains questions regarding birth indicators (e.g., birth weight, gestational age, birth complications), demographic information (e.g., race, ethnicity, parent education, parent occupation, family income), and siblings. The Family Information Form will be completed by the child's parent or guardian. The Family Information Form is attached.

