**7) Data Management\***

Paper forms will be used to collect consent and demographic/family history information as well as for the ASRS and ASQ assessments. Paper forms will be scanned and stored on a secure, encrypted cloud-based system (i.e., Box) and the forms will be physically stored in a locked file cabinet.

A unique subject identifier will be assigned and used for all OAE and ABR data acquisition. OAE and ABR data will be recorded on the data acquisition system, stored electronically identified by subject number only, and backed up daily to a secure computer at the University of Miami. A deidentified database (records will be identified by subject numbers only, names will not be included) containing all study data will be created and will be accessible only to authorized study personnel. Identifying information will not be included in the analyses nor released to non-study personnel. Deidentified raw OAE and ABR data will be transferred using a secured Box account to [name] at Intelligent Hearing Systems for review to assure that the data meet the required quality for the study.

Data analysis plan:

The following statistical analyses will be performed:

- 1) Analysis of variance and t-tests will be conducted to determine if there are significant differences between the ASD and control groups, sex and ear on ABR peak latency and amplitude.
- 2) Sensitivity and specificity measures will also be conducted using Receiver Operating Characteristic (ROC) curves and d-prime measures. The optimal stimulation rate for ASD detection will be determined using these measures.

Factor: Click stimulation rate (five levels): 19, 39, 61, 120, and 250 per second. The three lower rate levels were selected to replicate previous research. The upper levels were selected to obtain ABRs with discernible peaks while challenging the neural transmission of the auditory system.

Dependent Variables: Absolute peak latencies and amplitudes.

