Title:

Screening for Autism Spectrum Disorders Using Auditory Brainstem Responses

Number: NCT03971578

Date: May 30, 2019

Project Funded by NIH NIDCD SBIR Grant R43DC018430-01 to Intelligent Hearing Systems Corp.

Grant Title:

Screening Device for Autism Spectrum Disorders using High Stimulation Rate ABR with Continuous Loop Averaging Deconvolution

Statistical Analysis Plan

Hypothesis: The detection of neurological anomalies can be accentuated by increasing the physiological demand on neural pathways by increasing the stimulation rate (Fujikawa-Brooks et al., 2010) and therefore increasing the specificity and sensitivity of ABR testing for ASD screening.

Rationale: The purpose of this experiment is to demonstrate that higher stimulation rates, achieved using the CLAD technique (Delgado and Ozdamar, 2004), will show differences in ABRs between age-matched populations of children with and without ASD. Although the increase in rate will also increase peak latency and decrease amplitudes, the ASD population is expected to show a greater latency shift effect and increase the specificity and sensitivity of ABR testing for ASD screening. Previously, Fujikawa-Brooks et al. (2010) used a maximum rate of 61/sec and showed a significant rate effect. Because of the time constraints of a Phase I feasibility study, testing of the target population, newborns, is not possible because a confirmed ASD diagnosis will not be available for several years. The researchers recognize that there are age related differences in ABR latencies; however, these have been well documented in a normal population. The use of an age-matched control group will provide a comparison to control for normal developmental changes in ABR latencies.

Factor: Click stimulation rate (five levels): 19, 39, 61, 120, and 250 per second. The three lower rate levels were selected to replicate previous research. The upper levels were selected to obtain ABRs with discernible peaks while challenging the neural transmission of the auditory system.

Dependent Variables: Absolute peak latencies and amplitudes, and right-left ear differences of both.

Analysis: Analysis of variance and t-tests will be conducted to determine rate effects. Sensitivity and specificity measures will also be conducted for each rate at various

References:

Delgado, R.E., Özdamar, Ö. (2004). Deconvolution of evoked responses obtained at high stimulus rates, *Journal of the Acoustical Society of America*, 115:1242–1251.

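### No masking to ASD/control status is specified for identifying ABR peaks, the step from which every outcome is derived

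*Protocol*

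**What the plan says.** **How outcomes are obtained.** Protocol Section 5 (Lab Session, ABR) says "ABR data will be recorded and peaks identified and measured". It names no reader, marking rule, repeat reading or algorithm.

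**What depends on it.** The data analysis plan in Protocol Section 7 gives "Dependent Variables: Absolute peak latencies and amplitudes"; the SAP adds the right-left ear differences of both. On these, "Analysis of variance and t-tests will be conducted to determine if there are significant differences between the ASD and control groups". ROC and d-prime measures follow, and they are to select the optimal stimulation rate.

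**When group is known.** A formal diagnosis "is required for children to be part of the ASD group" (Section 4), and families are "screened over the phone to determine if they meet the inclusion criteria" (Section 5, Phone Screen) before they are invited to the lab.

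**Expected direction.** The SAP Rationale states that "the ASD population is expected to show a greater latency shift effect".

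**Nearest text to a safeguard.** Sections 7 and 16 store ABR files by subject number and describe the database as deidentified, explained as leaving names out. Raw OAE and ABR data go to the device company "for review to assure that the data meet the required quality for the study". No criteria for accepting or rejecting a recording are given. Neither document mentions masking or blinding of the tester, the peak reader, the quality reviewer or the analyst.

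**The concern.** A peak latency or amplitude exists only once a peak has been chosen on the waveform. Where that choice involves judgement, a reader who knows the child's group and the hypothesis can, without intending it, place peaks later in one group than in the other. The resulting difference looks exactly like the effect under study, and a larger sample does not remove it.

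It would enter the t-tests and ANOVA for group and the ROC and d-prime results. Because this is a feasibility study, it would also enter the case for the next phase.

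A secondary concern is the acceptance of recordings. If they can be rejected without fixed criteria by someone who could know the group, the analysed set may be selected differently in the two groups.

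**Working it through.** **Step 1. Is masking specified anywhere?** Setting the relevant sections side by side:

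- Section 5 describes peak identification in the passive, with no reader, method, place or time.
- Sections 4 and 5 together mean the study holds each child's group status before the ABR is recorded.
- Sections 7 and 16 remove names. They do not say that subject numbers carry no group information, or that peaks are marked from those files by someone without the group key.
- Automated output is described for the OAE test (Sections 5 and 9). No such statement is made for ABR peaks.

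The plan as written therefore permits group-aware marking, although it does not require it.

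**Step 2. Sensitivity of the results to a marking shift.** The documents give no SD, effect size, alpha or marking error, so there is no stated figure to reproduce. Inputs:

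- 50 children per group (Section 15).
- Assumed: two-sided 5% unpaired t-test, normal data with equal SD, no true difference.
- Assumed: marking moves the ASD-minus-control difference by *b* between-child SDs.

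Formulas:

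- SE of the difference = √(2/50) = 0.20 SD.
- Noncentrality = *b*/0.20. The rejection probability is that of a noncentral t with 98 degrees of freedom falling outside the 5% critical values.
- AUC = Φ(*b*/√2).

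| Assumed shift *b* (SD) | Noncentrality | Chance of p < 0.05 | AUC |
|---|---|---|---|
| 0 | 0 | 5.0% | 0.50 |
| 0.1 | 0.5 | 7.9% | 0.53 |
| 0.2 | 1.0 | 16.8% | 0.56 |
| 0.3 | 1.5 | 31.8% | 0.58 |

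For scale, a difference of about 1.96 × 0.20 = 0.39 SD just reaches p = 0.05, and (1.96 + 0.84) × 0.20 = 0.56 SD is detectable with 80% power.

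**Step 3. Which results would be affected?**

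- The group difference and AUC at any given rate are biased by any non-zero *b*.
- A shift that is the same at all five rates, in SD units, moves every rate's AUC equally and favours none. The choice of optimal rate is biased only if the shift differs by rate.
- Likewise, a shift of constant size in milliseconds cancels from the group difference in latency change between rates, and one that is equal in both ears cancels from the right-left differences. Those results are affected only by an uneven shift.

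**Step 4. With masking.** If marking and acceptance are done without knowledge of group, expectation cannot act differently on the two groups. Then *b* = 0 from this source, and the 5% rate per test is restored.

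**The case against.** The strongest reply is that the documents are silent, and silence does not show unmasked reading. Marking could be automated, since Section 2 aims at an automated device. The quality reviewer receives number-only files, and nothing says that person meets the child or is told the group. An independent monitor without a conflict of interest reviews the validity and quality of the ABR data (Data and Safety Monitoring Plan). On the higher rates the protocol says "The upper levels were selected to obtain ABRs with discernible peaks while challenging the neural transmission of the auditory system", which does not suggest that peaks are hard to find. The SAP's analysis sentence breaks off in the supplied text, and attachments such as the full monitoring plan were not available.

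Much of this stands. A reader might infer that the staff who recruited and tested the child also mark the peaks. The documents do not say so, nor do they say that marking is manual. A reader might also take the SAP's expectation as guidance to whoever marks the peaks; it is a study hypothesis. That marking is harder at 120 and 250/s is an inference from the SAP's remark that amplitude falls as rate rises; neither document states it. The company's review may well be masked in practice, so the acceptance step is secondary.

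What does not stand is that these points fill the gap. Removing names does not conceal group. The monitor has full access to study records, is not stated to be masked, and reviews quarterly, which does not prevent bias at the moment of marking. Automation would answer most of the point, but it is not stated for ABR.

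**Conclusion.** The point holds as a gap in the plan: masking to group is not specified at the step that generates every dependent variable, although group is known beforehand and the expected direction is written down. It goes beyond missing detail, because the plan could be followed to the letter with group-aware marking.

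The consequence is conditional. If marking involves judgement and is not masked, a systematic shift biases the group difference and the AUC. Assumed shifts of 0.1 to 0.3 SD would give false-positive rates of about 8% to 32% per test and AUCs of 0.53 to 0.58 where the truth is 0.50. These figures show sensitivity and do not predict a bias; nothing in the documents fixes the size of the shift. It would be tempting to conclude that the high rates would be favoured as optimal. That requires a shift that grows with rate, which the documents do not establish.

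**What to change.** State the following in Protocol Section 5 and in the SAP:

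1. Peaks are marked off-line, from files relabelled with random codes that carry no group information and read in mixed order.
2. Marking is done by existing staff, where possible not the person who tested that child, or by a fixed automated rule if one is available. If ABR marking is already automated, say so and describe the rule.
3. Decisions to accept or reject a recording are made on the same coded files against criteria fixed in advance. Rejections are logged, and reported by group and rate once the key is open.
4. The group key is opened only after the peak file is locked.

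This is a cheap improvement. Raw recordings are already stored by subject number, so it needs protocol and SAP wording and a relabelling step. It calls for no additional reader, and the tester need not be masked. The downside is the relabelling itself and that marking must be done off-line.
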